Adverse events	X	X	X	X	X	X	X	X	X	X	X	X	X	X	X	X	X	X	5.3.7
KCCQ		X		X		X		X									X	X	5.2.1
EQ-5D		X		X		X		X				X				X	X	X	5.6.1
HCRU		X	X	X		X		X		X		X		X		X	X		5.6.2
Urine Pregnancy Test ¹³	X	X	X	X		X		X		X		X		X		X	X		5.3.4.2
Safety lab Tests	X ¹⁴	X	X	X		X		X		X		X		X		X	X	X	5.3.4
NT-proBNP	X	X	X	X				X				X					X	X	5.5
High-sensitivity TroponinT		X																	5.5
HbA1c ¹⁵	X	X		X		X		X		X		X		X		X	X		-

Trial Period	Screening ¹	Randomised Treatment Period ²															Follow Up Period ³		Relevant CTP section
		2	3	4	5 Phone call	6	7 Phone call	8	9 Phone call	10	11 Phone call	12	13 Phone call	14	15 Phone call	16	EOT Visit	FU Visit ³	
Visit	1																		
Trial week	-3	1	4	12	22	32	42	52	64	76	88	100	112	124	136	148	EOT Visit	EOT + 30 days	
Days from Randomisation Visit window ⁴	-28 to - 4	1	29±7	85 ±7	155 ±7	225 ±7	295 ±7	365 ±7	449 ±7	533 ±7	617 ±7	701 ±7	785 ±7	869 ±7	953 ±7	1037 ±7	---	---	
Fasting status ⁵	NF	F	NF	NF	-	NF		NF	-	NF	-	NF	-	NF	-	NF	F	F	
Lipid profile panel		X						X				X					X	X	5.3.4
eGFR (CKD-EPI _{cr} formula)	X	X	X	X		X		X		X		X		X		X	X	X	5.3.4.1
UACR	X	X	X	X		X		X		X		X		X		X	X	X	5.3.4
PK sampling (substudy) ¹⁶				X															5.4.1
Sampling for biobanking of serum/plasma/urine/ DNA (optional, requires separate informed consent) ¹⁷		X ¹⁸		X				X											5.5.1
Dispense trial medication ¹⁹		X	X	X		X		X		X		X		X		X			4.1.4 6.2.2
Return Medication/ medication compliance check			X	X		X		X		X		X		X		X	X		4.3

1. The screening procedures can be done on different days within the time window.
2. From Visit 8 and onwards, on-site visits will be scheduled every 24 weeks until end of trial.
Patients who prematurely discontinue trial medication will perform EOT visit and Follow Up visit, and then continue with scheduled visits until the trial is stopped.
For patients not willing to attend scheduled visits, telephone calls must be made regularly (ref. [Section 3.3.4.1](#)) to document any occurrence of outcome events and vital status.
If the trial continues beyond 148 weeks, visits are to be repeated with same intervals as from week 64 and onwards.
3. Timepoint for the EOT will be communicated via an Investigator letter when the Sponsor is confident that required number of events will be reached within a reasonable timeframe (ref. [Section 3.1](#) and [6.2.3](#)). All patients will have a follow up visit 30 days following regular or premature completion of the treatment period.

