5.1.3 Further endpoints

- Time from first to second adjudicated HHF

Proprietary confidential information © 2019 Boehringer Ingelheim International GmbH or one or more of its affiliated companies

- Time to first all-cause hospitalisation
- Occurrence of adjudicated HHF within 30 days after first adjudicated HHF
- Occurrence of adjudicated HHF and CV death. This endpoint will account for clinical hierarchies in composite outcomes, i.e. CV death is ascribed greater importance than HHF (see win ratio in [Section 7.3.3](#))
- New onset of atrial fibrillation
- Adjudicated MI (fatal or non-fatal)
- Adjudicated stroke (fatal or non-fatal)
- Adjudicated TIA
- Composite of time to first event of all-cause mortality and all cause hospitalisation
- Composite of adjudicated CV death or adjudicated non-fatal MI
- Composite of adjudicated CV death or adjudicated non-fatal stroke
- Adjudicated CV death, adjudicated non-fatal MI, adjudicated non-fatal stroke (3-point MACE)
- Progression to macro albuminuria (defined as UACR >300 mg/g) from baseline for patients with baseline UACR ≤ 300 mg/g
- Time to first new onset of sustained normo- or micro albuminuria (UACR ≤ 300 mg/g) in patients with macro albuminuria at baseline
- Time to first new onset of sustained normo albuminuria (UACR < 30 mg/g) in patients with micro- or macro albuminuria at baseline
- eGFR (CKD-EPI)_{cr} change from baseline to 30 days after treatment stop
- Composite of sustained reduction of ≥40% eGFR (CKD-EPI)_{cr} or sustained eGFR (CKD-EPI)_{cr} <15 mL/min/1.73 m² (< 10 mL/min/1.73 m² for patients with eGFR (CKD-EPI)_{cr} < 30mL/min/1.73 m² at baseline), or adjudicated CV death
- Composite of sustained reduction of ≥40% eGFR (CKD-EPI)_{cr} or sustained eGFR (CKD-EPI)_{cr} <15 mL/min/1.73 m² (< 10 mL/min/1.73 m² for patients with eGFR (CKD-EPI)_{cr} < 30mL/min/1.73 m² at baseline), or all-cause mortality
- Composite of sustained reduction of ≥40% eGFR (CKD-EPI)_{cr} or sustained eGFR (CKD-EPI)_{cr} <15 mL/min/1.73 m² (< 10 mL/min/1.73 m² for patients with eGFR (CKD-EPI)_{cr} < 30mL/min/1.73 m² at baseline), adjudicated CV death, or adjudicated HHF

Proprietary confidential information © 2019 Boehringer Ingelheim International GmbH or one or more of its affiliated companies

- Change from baseline in KCCQ overall summary score at week 52
- Change from baseline in KCCQ total symptom score at week 52
- Change from baseline in KCCQ individual domains at week 52

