- Change from baseline in KCCQ based on patient-preferred outcome at week 52
- Change in NYHA class from baseline at week 52
- Change from baseline in Health-related quality of life measured by EQ-5D
- Health economic analysis by Health Care Resource Utilisation
- Changes in NT-proBNP from baseline over time
- Change in albuminuria from baseline over time
- Change in albuminuria from baseline over time by baseline UACR) categories (<30 mg/g, ≥30mg/g to ≤300mg/g, >300 mg/g)
- Incidence of acute renal failure (based on narrow SMQ)
- Time to first acute kidney injury (based on the preferred term)
- Change from baseline in body weight over time
- Change from baseline in Systolic Blood Pressure (SBP) over time
- Change from baseline in Diastolic Blood Pressure (DBP) over time
- Change from baseline in pulse rate over time
- Change from baseline in HbA1c over time in the overall population and in 3 subgroups (non-DM, pre-DM, and DM)

Refer to the trial statistical analysis plan (TSAP) for the complete set of further endpoints.

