5.5 ASSESSMENT OF BIOMARKERS

Samples for NT-proBNP will be collected at Visit 1 (Screening) to determine whether the patient is eligible for the trial. Further samples for NT-proBNP will be collected at later time points in the trial (see [Flow Chart](#)) to investigate a potential effect of the trial medication. Samples for NT-proBNP will be analysed at the Central Laboratory.

Samples for the determination of high-sensitivity cardiac troponin T will be collected at Visit 2 (Randomisation) and analysed at the Central Laboratory.

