7.3 PLANNED ANALYSES

The primary efficacy analysis will be based on the randomised set (RS), including all randomised patients.

The safety analysis will be based on the treated set (TS), which consists of all patients treated with at least one dose of the trial medication.

For both efficacy and safety analyses, treatment will be evaluated as randomised.

For serum creatinine and values based on upon this measurement such as eGFR, baseline will be defined as the mean of all available measurements from the screening visit until start of randomised trial medication.

Baseline status of DM is defined as:

- DM: any pre-treatment HbA1c above 6.5 or history of DM as entered in the eCRF on the medical history page
- Pre-DM: no history of DM and no HbA1c ≥ 6.5 before treatment and a pre-treatment HbA1c value of ≥ 5.7 and < 6.5
- Non-DM: not meeting criteria of DM or pre-DM above

For all other endpoints, baseline will be defined as the last available measurement before start of randomised trial medication.

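### For UACR and NT-proBNP, section 7.3 uses only the last pre-dose value although two are scheduled: a free precision gain for further endpoints, not an error

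*Protocol*

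**What the plan says.** Protocol section 7.3 (Planned Analyses) has two baseline rules. For serum creatinine and quantities derived from it, such as eGFR, "baseline will be defined as the mean of all available measurements from the screening visit until start of randomised trial medication". For the rest, "For all other endpoints, baseline will be defined as the last available measurement before start of randomised trial medication". UACR rests on urine creatinine, so it falls under the second rule, as does NT-proBNP. Version 1.0 and the amended protocol word both rules alike.

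The Flow Chart schedules UACR, NT-proBNP and HbA1c at Visit 1 (screening) and again at Visit 2 (randomisation).

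Section 5.1.3 (Further endpoints) uses these baselines in several places:
- "Progression to macro albuminuria (defined as UACR >300 mg/g) from baseline", restricted to patients at or below 300 mg/g at baseline.
- Two endpoints on sustained return to a lower albuminuria class, restricted to patients above 300 mg/g and to patients with micro- or macroalbuminuria at baseline.
- "Change in albuminuria from baseline over time by baseline UACR) categories", with cut-points at 30 and 300 mg/g.
- "Changes in NT-proBNP from baseline over time".

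Section 7.3.3 analyses the continuous further endpoints by MMRM with a baseline-by-visit term. On Visit 1 NT-proBNP, section 5.5 states: "Samples for NT-proBNP will be collected at Visit 1 (Screening) to determine whether the patient is eligible for the trial".

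**The concern.** Where two pre-treatment values of a variable marker exist, their mean lies closer to the patient's usual level than either value alone. Section 7.3 applies that principle to creatinine, from the same two visits, and gives no reason for dropping it elsewhere.

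Two things are given up. First, a noisier baseline covariate explains less of the outcome, so the confidence interval for the treatment effect on albuminuria and NT-proBNP is wider than it could be. Second, baseline UACR decides who enters the progression and regression analyses and which UACR category a patient is reported in. A patient whose single sample falls on the wrong side of 30 or 300 mg/g joins the wrong group, and later movement back to the usual level then looks like progression or regression.

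**Working it through.** **What the protocol gives.** It states no SD, within-patient variability or misclassification rate for UACR or NT-proBNP, so there is no stated figure on this point to reproduce. The sizing in section 7.7 (841 events, 4126 patients) does not depend on the baseline rule. All SDs below are assumptions, on the natural-log scale.

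**1. UACR, precision.** Let tau be the between-patient SD, s the within-patient SD, c the SD of true change from baseline to follow-up, and k the number of baseline values averaged. The residual variance after adjusting for baseline is

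(tau² + s² + c²) − tau⁴ / (tau² + s²/k).

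With tau = 1.5 (tau² = 2.25, tau⁴ = 5.0625):

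| s | c | k = 1 | k = 2 | Reduction |
|---|---|---|---|---|
| 0.3 | 0 | 0.1765 | 0.1341 | 24% |
| 0.3 | 0.4 | 0.3365 | 0.2941 | 13% |
| 0.3 | 0.8 | 0.8165 | 0.7741 | 5% |
| 0.6 | 0 | 0.6703 | 0.5267 | 21% |
| 0.6 | 0.4 | 0.8303 | 0.6867 | 17% |
| 0.6 | 0.8 | 1.3103 | 1.1667 | 11% |

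The first row in full: k = 1 gives 2.34 − 5.0625/2.34 = 0.1765; k = 2 gives 2.34 − 5.0625/2.295 = 0.1341; and 1 − 0.1341/0.1765 = 24%. The gain shrinks as c grows, and c = 0 (no patient's true level ever changes) is an extreme.

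A second route uses only the correlation r between any two measurements. Residual variance is 1 − r² with one baseline and 1 − 2r²/(1 + r) with the mean of two. At r = 0.5 these are 0.750 and 0.667, a standard error 5.7% lower. At r = 0.9 they are 0.190 and 0.147, a standard error 11.9% lower.

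**2. UACR, class.** Simulation with median 25 mg/g, tau = 1.5 and cut-points 30 and 300 mg/g compares the baseline class with the class of the patient's usual level.

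| s | One value, wrong class | Geometric mean of two, wrong class |
|---|---|---|
| 0.3 | 8% | 6% |
| 0.6 | 16% | 11% |

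A wider grid (median 20–30, tau 1.3–1.6, s 0.3–0.7) gives 7–20% against 5–14%. Among patients whose baseline exceeds 300 mg/g, the share whose usual level is at or below 300 is 19% (s = 0.3) to 39% (s = 0.6) with one value, and 13% to 27% with the mean of two.

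**3. NT-proBNP.** Visit 1 is selected by the entry cut-off, so it tends to lie above the patient's usual level. Simulation with selection at 300 pg/ml (medians 500–900, between-patient SD 0.8, s 0.2–0.5) puts the Visit 2 value at about 0% bias and the Visit 1/Visit 2 mean 0.5% to 6.7% too high. Averaging is therefore the wrong remedy here. Keeping Visit 2 as baseline and adding log Visit 1 as a second covariate avoids that bias. With medians 600–1000, s 0.2–0.4 and c 0.2–0.4, it is worth about 8% to 19% more patients in precision. The 900 pg/ml cut-off for patients with AF was not modelled.

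**The case against.** The strongest reply is that nothing here is wrong. The last value before first dose is a conventional, clear baseline, fixed before treatment and applied alike to both arms, so regression to the mean falls equally on both. All affected analyses are further endpoints outside the hierarchy in section 7.2. Averaging creatinine can be read as a deliberate exception, because eGFR is a model covariate and underlies a key secondary endpoint. All of that stands, and it is why this is an improvement and not an error.

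A second reply is that Visit 2 better reflects the state at first dose: Visit 1 may be up to 28 days earlier, and oral diuretics need be stable for only one week before Visit 2. This carries limited weight for UACR, since section 7.3 accepts the same Visit 1 sample for creatinine. For NT-proBNP the last value is the right baseline, for the separate reason that Visit 1 is the selection value.

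A third reply is that the regression endpoints require a sustained change, which dampens single-sample noise after baseline. That is so, but entry to those risk sets still rests on one sample, and the progression endpoint carries no such wording.

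A reader might also infer that the plan demonstrably misfiles patients, or that the trial needs more patients. The documents support neither: they give no UACR distribution or variability, and the trial is not sized on these markers.

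**Conclusion.** The point holds as a costless improvement to further endpoints. For UACR, residual variance falls by about 5% to 24% as the SD of true change runs from 0.8 down to 0, and class misassignment falls from about 8–16% to 6–11%. Averaging reduces the class noise but does not remove it. For NT-proBNP the gain from the extra covariate is about 8% to 19% in patient-equivalent precision. Every figure rests on assumed SDs, and the formula ignores the other MMRM covariates. Alpha, the 841 events, the 4126 patients and the primary and key secondary analyses are unaffected.

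It would be tempting to extend the point to HbA1c, which is also measured twice. No gain was quantified there, and diabetes status already draws on every pre-treatment value ("DM: any pre-treatment HbA1c above 6.5 or history of DM as entered in the eCRF on the medical history page"), so an averaged HbA1c baseline is optional.

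**What to change.** In section 7.3, and matching in the SAP before unblinding:

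- **UACR:** define baseline as the geometric mean of all valid central-laboratory values from screening to first dose. Exclude results replaced on re-test as spurious or beyond stability (section 3.3). Use this baseline for change from baseline, the baseline-by-visit term, the progression and regression risk sets, and the three UACR categories.
- **NT-proBNP:** keep the last pre-dose value as baseline for change, and add log Visit 1 NT-proBNP as a second baseline covariate in the MMRM.
- **HbA1c:** the mean of pre-treatment values is optional.

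The cost is wording and a small change to the derivation of baseline variables. No visit or sample is added, since both measurements are already in the Flow Chart.

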7.3.1 Primary endpoint analyses

The primary endpoint will be evaluated on the randomised set using a Cox proportional hazards model with treatment, age (continuous), gender, geographical region, baseline status of DM (DM, pre-DM, no DM), LVEF (continuous) and eGFR (CKD-EPI)_{cr} at baseline (continuous) as covariates.

The time to the event of interest will be computed as (event date – randomisation date) + 1. All events observed after randomisation until completion of the planned treatment phase will be included in the analysis. Patients who do not have an event will be censored at the individual end of the planned treatment phase or the last day that the patient was known to be free of the event, whichever is earlier. The time to censoring will be computed as (individual end of the planned treatment phase or the last day known to be free of the event – randomisation date) + 1. For patients who have more than one primary endpoint event during the trial, the time to the first occurrence of the primary endpoint event will be considered for the primary analysis. Only the adjudicated and confirmed events will be used for the primary analysis.

Proprietary confidential information © 2019 Boehringer Ingelheim International GmbH or one or more of its affiliated companies

To detect any heterogeneity in the treatment effect among diabetic patients, pre-diabetic patients and non-diabetic patients, a subgroup analysis will be performed by including the diabetic status by treatment interaction term into the Cox model.

Standard subgroup analyses of the primary endpoint include geographical region, sex, BMI, LVEF, renal function, prognostic factors, age, ethnicity, race and different background therapies etc. More details will be specified in the TSAP.

A sensitivity analysis will be provided based on the TS only including any events up to 30 days after treatment discontinuation.

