3.3.2 Inclusion criteria

1. Age \geq 18 years at screening. For Japan only: Age \geq 20 years at screening
2. Male or female patients. WOCBP^a must be ready and able to use highly effective methods of birth control per ICH M3 (R2) [[R09-1400](#)] that result in a low failure rate of less than 1% per year when used consistently and correctly. A list of contraception methods meeting these criteria is provided in the patient information
3. Patients with chronic HF diagnosed for at least 3 months before Visit 1, and currently in HF NYHA class II-IV
4. Chronic HF with preserved EF defined as LVEF > 40 % per local reading (obtained by echocardiography, radionuclide ventriculography, invasive angiography, MRI or CT), and no prior measurement of LVEF \leq 40% under stable conditions^b. A historical LVEF may be used if it was measured within 6 months prior to visit 1, and more than 90 days after any myocardial infarction (as defined in exclusion criterion No.1) or the LVEF may be measured after study consent has been obtained. The LVEF must be documented in an official report prior to randomization.

^aWomen of childbearing potential are defined as:

- having experienced menarche and
- not postmenopausal (12 months with no menses without an alternative medical cause) and
- not permanently sterilised (e.g., hysterectomy, bilateral oophorectomy or bilateral salpingectomy).

^b In the Investigator's opinion

Proprietary confidential information © 2019 Boehringer Ingelheim International GmbH or one or more of its affiliated companies

5. Elevated N-terminal of the prohormone brain natriuretic peptide (NT-proBNP) > 300 pg/ml for patients without AF, OR > 900 pg/ml for patients with AF, analysed at the Central laboratory at Visit 1
6. Patients must have at least one of the following evidence of HF:
 - a. Structural heart disease^c (left atrial enlargement and/or left ventricular hypertrophy) documented by echocardiogram at Visit 1 or within 6 months prior to Visit 1, OR
 - b. Documented HHF^d within 12 months prior to Visit 1
7. Oral diuretics, if prescribed to patient according to local guidelines and discretion of the Investigator, should be stable for at least 1 week prior to Visit 2 (Randomisation)
8. Body Mass Index (BMI) < 45 kg/m² at Visit 1
9. Signed and dated written ICF in accordance with GCP and local legislation prior to admission to the trial

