7 STATISTICAL METHODS AND DETERMINATION OF SAMPLE SIZE

7.1 STATISTICAL DESIGN – MODEL

The eligible patients for this trial will be randomised to empagliflozin 10 mg and placebo in 1:1 ratio, stratified by geographical region, status of DM (DM, pre-DM, no DM), LVEF (<50%, ≥50%) and eGFR (CKD-EPI)_{cr} (<60 mL/min/1.73 m², ≥60 mL/min/1.73 m²) at screening visit.

To ensure the trial population consist of a reasonable combination of non-, pre- and DM patients, and to aim for approximately 35% to 50% of the population or more with an LVEF ≥50% capping will be used on trial level (see also [Section 3.3](#)). Capping on regional level may be applied to achieve a contribution of each region to each category of diabetes status.

The composite primary endpoint is the time to first event of adjudicated CV death or adjudicated HHF. The statistical model for the primary analysis is the Cox proportional hazards model. The hazard ratio and its confidence limits will be determined for evaluating the superiority of empagliflozin to placebo for the primary endpoint.

The key secondary endpoints, which are part of the testing strategy, are

- occurrence of adjudicated HHF (first and recurrent), and
- eGFR (CKD-EPI)_{cr} slope of change from baseline

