7.2 NULL AND ALTERNATIVE HYPOTHESES

A hierarchical testing procedure will be followed for the assessment of the primary and the key secondary endpoints. For all endpoints, superiority of empagliflozin vs. placebo will be evaluated with a two-sided test in the following structure:

Null hypothesis: There is no difference between the effect of placebo and the effect of empagliflozin in terms of the endpoint in question.

Alternative hypothesis: There is a difference between the effect of placebo and the effect of empagliflozin in terms of the endpoint in question. The tests will be performed in the following hierarchical order:

1. Time to first event of adjudicated CV death or adjudicated HHF
2. Occurrence of adjudicated HHF (first and recurrent)
3. eGFR (CKD-EPI)_{cr} slope of change from baseline

Starting from step 1, if the null hypothesis is rejected, and the result is more favourable for empagliflozin, superiority is concluded in the tested endpoint, and the overall type I error is preserved for the test in the next step. If at any step the null hypothesis is not rejected, subsequent tests are conducted in an exploratory fashion.

Proprietary confidential information © 2019 Boehringer Ingelheim International GmbH or one or more of its affiliated companies

The overall type one error rate will be preserved at a level of 0.05 (2-sided). The type one error rate used at the final analysis will be influenced by the pre-planned interim analysis – see [Section 7.4](#).

In the final analysis after the evaluation of recurrent HHF, alpha will be split into 0.001 to be used for the analysis of eGFR slope, and the rest will be transferred to the meta-analyses.

In case the trial is finished early at the time of interim analysis, using $\alpha_{interim}$ for the primary and key-secondary endpoints in the testing hierarchy according to the α -spending function in [Section 7.4](#), the following α -split will be used for eGFR slope analysis and the meta-analyses:

- 0.1 * $\alpha_{interim}$ will be used for the eGFR slope analysis and
- 0.9 * $\alpha_{interim}$ will be transferred to the meta-analyses

In both the interim and final analyses, if the slope analysis is successful, the alpha of this branch will then be transferred to the meta-analyses.

The testing hierarchy is summarised in Figure 7.2: 1 showing the alpha-spending at the final analysis.

[figure not shown]

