7.3.2 Secondary endpoint analyses

The key secondary endpoints occurrence of adjudicated HHF (first and recurrent) will be modelled using a joint frailty model together with adjudicated CV death in order to take into account the dependence between the endpoints. The joint frailty model will be adjusted for the same covariates as the primary analysis.

The joint frailty model therefore models the hazards in the following way:

$$r_i(t | \omega_i, Z_i) = \omega_i \exp \{ \beta'_1 Z_i \} r_0(t)$$

$$\lambda_i(t | \omega_i, Z_i) = \omega_i^\alpha \exp \{ \beta'_2 Z_i \} \lambda_0(t)$$

where $r_i(t)$ is the hazard of the recurrent HHF for the i th patient, proportional to the baseline intensity function r_0 . The hazard function of CV death for the i th patient is λ_i proportional to the baseline hazard λ_0 . β_1 and β_2 are vectors of the regression coefficients of the covariate vectors Z_i including treatment, age (continuous), gender, history of DM, geographical region, LVEF (continuous) and eGFR (CKD-EPI)_{cr} at baseline (continuous). Patient specific independent random effects are denoted by ω_i , with α giving the relation between HHF and CV death.

Patient specific independent random effects denoted by ω_i and are assumed to follow a gamma distribution with mean 1.

The resulting likelihood function can be solved assuming piecewise constant hazards.

Slope in change from baseline of eGFR (CKD-EPI)_{cr} will be analysed by a random coefficient model allowing for random intercept and random slope per patient. The model will include the factors treatment, gender, geographical region, and status of DM as fixed effects and eGFR (CKD-EPI)_{cr} at baseline (continuous), LVEF (continuous), age (continuous), time, interaction of treatment by time and interaction of eGFR (CKD-EPI)_{cr} at baseline (continuous) by time as linear covariates and allow for randomly varying slope and intercept between patients. The model will include all on-treatment change from baseline data.

Since the slope is run on the change from baseline data, the intercept will model the acute drop, whereas the long-term effect is modelled by the slope.

Proprietary confidential information © 2019 Boehringer Ingelheim International GmbH or one or more of its affiliated companies

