7.7 DETERMINATION OF SAMPLE SIZE

For the sample size calculation, a yearly event rate in the placebo group of 10% is assumed. The assumption is based on the CHARM-Preserved study and part of the TOPCAT study from the Americas [[R07-4374](#), [R16-1458](#)]. The annual event rates in CHARM-Preserved were 8.1% in the candesartan group and 9.1% in the placebo group. The annual rates from the Americas in the TOPCAT study were 10.4 in the spironolactone group and 12.6 in the placebo group.

The trial is designed to achieve a power of 90% for a two sided test at level $\alpha = 0.05$.

Proprietary confidential information © 2019 Boehringer Ingelheim International GmbH or one or more of its affiliated companies

The following table presents the number of required events together with the number of to be randomised and treated patients assuming an accrual period of 18 months and a follow-up period of 20 months for different assumed true hazard ratios. However, the follow-up period is not fixed but the trial will continue until the necessary number of events has been observed, which are confirmed by the adjudication committee.

The drop-out rate from the trial is assumed to be low (< 1% per year) and is therefore not further considered for the determination of sample size.

Table 7.7: 1 Sample size calculation – not including interim analyses:

Yearly event rate for HHF+CV Death (Placebo)	Hazard ratio	Number of events for 90% power for HHF+CV Death	Number of patients for 18 months accrual and 20 months follow up
10%/Year	0.70	331	1710
10%/Year	0.75	509	2562
10%/Year	0.80	841	4126
10%/Year	0.85	1601	7656
10%/Year	0.90	3814	17814

A hazard ratio of 0.8 was chosen as a conservative estimate based on the results of the EMPA-REG OUTCOME trial described in [Section 1.2.3](#)

Therefore, at least 841 confirmed primary events should be observed and at least 4126 patients should be randomised and treated in order to achieve a power of 90% assuming a true hazard ratio of 0.8.

Including interim analysis with Hwang-Shih-deCani alpha spending with gamma=8 at 60% of information will diminish the power only slightly to 89.98%.

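### Adjusting the primary Cox model for baseline NT-proBNP could add roughly 0 to 4 power points from data already collected; the planned model is valid without it

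*Protocol*

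**What the plan says.** All references are to the current protocol (revision of 20 Nov 2019).

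- **Primary model.** Section 7.3.1 lists the covariates in full: "treatment, age (continuous), gender, geographical region, baseline status of DM (DM, pre-DM, no DM), LVEF (continuous") and baseline eGFR (continuous). The list is closed in the protocol and not left to the TSAP.
- **Stratification.** Sections 7.1 and 7.6 stratify by region, diabetes status, LVEF and eGFR. All four are in the model. Age and gender are in the model too, but are not strata.
- **NT-proBNP.** Inclusion criterion 5 (Section 3.3.2) requires a value above "300 pg/ml for patients without AF, OR > 900 pg/ml for patients with AF, analysed at the Central laboratory at Visit 1". The Flow Chart schedules a further sample at Visit 2. Section 5.5 gives the purpose of the first sample: "Samples for NT-proBNP will be collected at Visit 1 (Screening) to determine whether the patient is eligible for the trial". Later samples serve to look for a drug effect.
- **Where the model is reused.** For recurrent HHF, Section 7.3.2 says: "The joint frailty model will be adjusted for the same covariates as the primary analysis". Section 7.4 takes the interim p-values for the primary endpoint and for CV death from the primary Cox model.
- **Design figures.** Section 7.7: "The trial is designed to achieve a power of 90% for a two sided test at level" 0.05, with a hazard ratio of 0.80, 841 events and 4126 patients. Nothing in that section credits the design with a gain from covariate adjustment.

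**The concern.** When a Cox model leaves out a baseline variable that predicts the event, the treatment hazard ratio it estimates lies closer to 1 than the ratio from a model that includes the variable. Putting the variable in moves the estimate away from 1, and the test usually gains some power at the same number of events.

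NT-proBNP is a natural candidate. It is measured in one central laboratory, it must be available for a patient to be eligible, and it is taken before treatment starts. The sponsor also already adjusts for two variables that are not strata, so a rule of adjusting only for strata does not explain its absence. What is at stake is some power for the primary test, obtainable without more patients, events or measurements.

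**Working it through.** **1. The plan's own figures.** Inputs from Section 7.7: hazard ratio 0.80, two-sided level 0.05, power 90%, 1:1 allocation, placebo risk 10% per year, 18 months' accrual plus 20 months' follow-up.

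- Events (Schoenfeld): 4 × (1.960 + 1.282)² / (ln 0.80)² = 4 × 10.507 / 0.04979 = 844.1, so 845. Freedman's formula gives 852. The plan states 841.
- Power at 841 events: Φ(√841/2 × 0.2231 − 1.960) = Φ(3.236 − 1.960) = 89.9%; at level 0.0496 it is 89.8%.
- Patients: yearly hazard λ = −ln 0.9. Event probability is 1 − (e^(−λf) − e^(−λ(a+f)))/(λa), with a = 1.5 and f = 20/12 years. This gives 0.2240 on placebo and, with 0.8λ, 0.1837 on empagliflozin. Then 841/(0.2240 + 0.1837) = 2062.6, so 2063 per arm and 4126 in total, exactly as stated.

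The design therefore reproduces with no NT-proBNP term.

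**2. What adjustment would add.** The protocol gives no prognostic strength for NT-proBNP, so it is assumed over a range. It is expressed as the hazard ratio per standard deviation (SD) of log NT-proBNP. Two simulations were run. Both used 4126 patients, uniform accrual over 18 months, analysis at the 841st event, and a treatment hazard ratio of 0.80 conditional on NT-proBNP.

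*Simulation A:* 2800 trials per setting, other covariates with combined SD 0.35 on the log-hazard scale, one-sided level 0.0248. Strength is defined given the planned covariates.

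| HR per SD | Mean HR, NT-proBNP omitted | Power omitted | Power included | Gain (points) |
|---|---|---|---|---|
| 1.3 | 0.801 | 89.2% | 89.4% | 0.2 |
| 1.6 | 0.804 | 87.7% | 89.7% | 2.0 |
| 2.0 | 0.811 | 85.5% | 89.4% | 3.9 |

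*Simulation B:* 1600 trials per setting, NT-proBNP as the only covariate, one-sided level 0.025. The Monte Carlo standard error of each power is about 0.8 points.

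| HR per SD | Mean HR omitted / included | Power omitted | Power included | Gain (points) |
|---|---|---|---|---|
| 1.22 | 0.802 / 0.801 | 89.9% | 90.0% | 0.1 |
| 1.49 | 0.802 / 0.799 | 89.6% | 90.2% | 0.6 |
| 1.82 | 0.809 / 0.802 | 86.1% | 88.5% | 2.4 |
| 2.23 | 0.814 / 0.800 | 85.5% | 89.8% | 4.3 |

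As a cross-check, the omitted-model hazard ratios of simulation B (0.8015, 0.8023, 0.8085, 0.8141) in the Schoenfeld power formula give 89.4%, 89.1%, 86.9% and 84.7%. These agree with the simulated powers to within Monte Carlo error.

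**3. Validity.** With a true hazard ratio of 1, the model without NT-proBNP rejected in 4.1% to 5.5% of trials at the two-sided 5% level (standard error about 0.5 points). The omission does not disturb the type I error.

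**The case against.** The strongest reply is that nothing is broken. The model is fully pre-specified, includes every stratification factor, and gives a valid test. The hazard ratio without NT-proBNP is a slightly less conditional quantity, not a biased one, and the shift is small because only about 20% of patients (841/4126) have an event. All of this stands.

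A reader might also infer that part of the promised 90% power is missing. The protocol does not support that. Section 7.7 says "A hazard ratio of 0.8 was chosen as a conservative estimate based on the results of the EMPA-REG OUTCOME trial described in" its Section 1.2.3, and nowhere makes the 0.80 conditional on NT-proBNP. If 0.80 is the hazard ratio of the planned model, the planned power is intact and adjustment comes on top. The omitted-covariate powers in the tables fall short only because the simulations set 0.80 as the conditional ratio.

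Three further readings go beyond the documents:

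- *That the protocol contradicts itself by measuring NT-proBNP to establish risk and then ignoring it.* Section 5.5 gives eligibility as the purpose.
- *That the gain carries over to recurrent HHF and all secondary endpoints.* The joint frailty model already has a patient-level random effect for unmeasured heterogeneity, and no gain was simulated for it. The other secondary endpoints are exploratory, and some (diabetes onset, the renal composite) have no shown link to NT-proBNP.
- *That HHF in the previous 12 months belongs in the model on the same grounds.* In inclusion criterion 6 it is an alternative to structural heart disease, and no gain was calculated for it.

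What remains against the reply is that the gain, though uncertain, comes from a baseline value that every patient already has.

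**Conclusion.** The omission is real and worth changing as an efficiency improvement. It is not an error. The expected gain for the primary test is well under 1 power point at about 1.3 per SD, about 2 points at 1.6 to 1.8, and about 4 points at 2.0 to 2.2.

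The result rests on two assumptions: a treatment hazard ratio of 0.80 conditional on NT-proBNP, and a prognostic strength that the protocol does not provide. That strength must be read as what remains after age, eGFR and the other planned covariates. Simulation B had no other covariates, so a given raw strength would yield less than its table shows wherever the information is shared. The documents cannot say which row applies.

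**What to change.** Before the interim unblinding, add log-transformed baseline NT-proBNP to the Section 7.3.1 covariates, together with baseline AF status, because the entry cut-offs differ by AF. Use the Section 7.3 baseline rule (last value before trial medication), so that the Visit 1 value stands in where the Visit 2 value is missing. Keep the present model as a sensitivity analysis. If the interim has already been unblinded, specify the adjusted model as supportive only. HHF within the previous 12 months is an optional extra, and only if it is recorded for all patients.

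No new data or patients are needed, but the change is more than one line of wording:

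- The primary hazard ratio becomes slightly more conditional.
- The model behind both interim p-values in Section 7.4, including the one for CV death, changes with it.
- Consistency with the pooled analysis with trial 1245.121 (Section 7.3.6) has to be checked.
- Sections 7.3.2 and 7.3.3 tie the joint frailty model and the other Cox analyses to the primary model. The amendment should say whether they take on the new terms.
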